6.1 Treatment – Device

6.1.1 Intended Use for Device

The intended use of the ‘u-Smell-it’™ olfactory test device is to in a quantitative, fast and repeated manner rapidly determine if an individual has a loss of smell and if so, based on the score and the precision of the device determine the likelihood that s/he is at risk of being positive for SARS-CoV-2. This result would in turn serve as a quantitative indicator to guide judicious action (analogous to how temperature is used to truly identify a fever vs. patient self-identification) – e.g. a follow up PCR test. The comparative gold standard (most used) is the question of if the person believes that s/he has “a new loss of smell or taste”, as currently stipulated by the CDC (whether performed in a written or electronic questionnaire). While there are other smell based test kits they are either very long (10-15 min) and tedious (UPSIT) and will not be suitable for wide-scale rapid testing, or for the rapid 3-item SIT are non-variable, and as such will not be a blinded test, especially for repeated testing. Thus, we will compare the performance of our *u-Smell-it* test to the user-identified stated “new loss of smell/taste” – and anticipate a real unbiased test to greatly outperform a highly subjective assessment. A related underlying hypothesis that we seek to test in this trial is that COVID19+ people perform poorly in self-assessments and grossly underestimate their loss of smell. If this premise is validated AND the performance of the device is statistically high (especially in terms of sensitivity) then one would seek FDA approval under emergency authorization use (EUA). If this eventually clears the FDA then it would be used in wide scale US testing at the state and federal level.

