5.2 Outcome Variables

5.2.1 Primary Outcome Variables

The subject's score on using the olfactory device will be compared to the PCR results (**SARS-CoV-2 negative or positive**) on COVID19 outpatients. As the '*u-Smell it*' test has a variable scale (0-5) the ideal cutoff will be determined to maximize any one (or combination) of these factors:

- Sensitivity

- Specificity
- Accuracy

We will compare the performance of the smell test to the current CDC metric of self-described assessment of smell loss (the de facto standard – e.g. “I have a new loss of smell or taste”) in terms of sensitivity, specificity and accuracy. Repeatability will also be examined in a test-retest score conducted within 24 hours in a random subset of 25 asymptomatic HCW with a second device in which the order of the odorants is altered.

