6.2.1 Efficacy

The olfactory test enabled from the device will be compared to:

- Patient self-identification for loss of smell: “Do you have any new loss of smell or taste?” YES or NO.
- PCR results for the presence of SARS-CoV-2

The methods for the assessment will be statistical, as described above.

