6.3 Study Procedures

For the outpatient drive-up studies the following protocol steps will be performed.

1. As patients drive-up and are still in the car with the windows closed a HCW with suitable PPE will place a ziplock pouch under the wiper of the driver's side windshield. The bag will contain the following materials:
 - a. A consent form
 - b. A pre-sharpened 'golf-pencil'
 - c. The 'u-Smell-it' olfactory device test card
 - d. A multiple choice answer form
2. While in the car, if the patient consents, they will sign the consent form, read the simple instructions (which are also shown as pictograms to make it very easy to follow), take the test, and fill in the answers. This process will take about 1 minute.
 - a. Description of the test: The test card device has 5 windows each printed with a different scent (or no scent) and marked #1, 2, 3, 4, and 5. The test subject merely needs to use their pencil to scratch back and forth 3 times the first window, sniff the window, and looking at the answer score sheet pick the best choice of five choices and fill in the multiple choice circle ("no scent", and scent A, B, C or D). For instance this could be: no scent / apple / orange /

cherry /banana / rose. This procedure will be repeated for each of the 5 windows.

- b. The subject will also be asked on the test if:
 - i. "Do you have any new loss of taste or smell?" (Yes/No)
 - ii. "Does anything smell different in the last year?" (Yes/No)
 - iii. Do you have a stuffy or runny nose? (Yes/No)
- c. If the test site is not part of EPIC the patient will be asked their gender and age band (18-29, 30-39, 40-49, 50-59, 60-69, 70-79, 80+)

3. After the patient completes the test they will pull out the **Consent and Multiple choice questionnaire form**, and with the window still CLOSED hold it up to the driver's side window and it will then be photographed by the attending HCW (likely an ENT resident doctor) whom will add the unique identifier number and add it to the EPIC system.

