 - a. [Alternative should there be any issues with the camera or the patient must get out of the car]: The patient will take the completed test packet, place it back in the pouch and under the windshield. The HCW will take the packet and remove the **Consent Form** and **Multiple choice questionnaire form**, check if it is completed (if ask the patient), and place all remaining materials in a biohazard box for destruction. The Consent form and the Questionnaire will be digitalized (scan or photographed) and linked with EPIC so as to be compared to the PCR test results.
4. Information from the uploaded and **Multiple choice questionnaire form** will be entered by a person authorized to access the information into a table that includes:
 - a. Unique identifier
 - b. Gender
 - c. Age band (10 year)
 - d. Y/N to patient self-identified new loss of smell or taste
 - e. Y/N to patient response to "things in the last year smell different"
 - f. Y/N to patient self-identified blocked or stuff nose
 - g. Individual answers on the 5 window smell test
 - h. RT-PCR results for SARS-CoV-2 (+, - or Inconclusive)
 - i. Any other tests for COVID19 (CT or Serological) if given
5. The data will be analyzed in the following fashion:
 - a. Patients that report a blocked or stuffy nose will be excluded from the main analysis (as COVID-19 loss of smell is not due to nasal congestion); but will be analyzed separately to see how this would confound any interpretation.
 - b. Patients that are denoted SARS-CoV-2 "inconclusive" will be excluded from the main analysis; but will be separately analyzed to see if they colocalize with normosmia or anosmia.
 - c. Patients will be split into SARS-CoV-2 positive and negative. As the negative pool is likely to be much larger it will be statistically matched by gender and age profile (potentially with larger bands – e.g. 20 year, depending on the sample size)

- d. The + and - SARS-CoV-2 groups individual performance on the smell test (score 0-5) will be plotted as a histogram. A cutoff will best be chosen to segregate people with normosmia and anosmia (e.g. score = 2 or 3).
- e. False Positives (FP) and False Negatives (FN) will be identified and used to measure the selectivity and sensitivity, respectfully.
- f. Based on the statistical performance (see Table 1) we will determine when we have enough patients to complete the study with a given value of precision.

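### The designated self-report item combines smell and taste, so the plan can bound but not measure how far PCR-positive people under-report loss of smell

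*Combined protocol and SAP*

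**What the plan says.** Section 6.1.1 puts forward, as something this trial will test, that "COVID19+ people perform poorly in self-assessments and grossly underestimate their loss of smell". It makes that premise, together with strong device performance, the condition for later seeking emergency authorization.

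The self-report set against the card is one Yes/No item. On the answer form (6.3, step 2b-i) it reads "Do you have any new loss of taste or smell"; in 6.2.1 it reads "Do you have any new loss of smell or taste". It is stored as one field (6.3, step 4d): "Y/N to patient self-identified new loss of smell or taste".

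Two sections describe this combined item as if it were about smell alone. Section 5.2.1 calls it "the current CDC metric of self-described assessment of smell loss", and 6.2.1 introduces it as "Patient self-identification for loss of smell".

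The form has one other self-report item on smell, "Does anything smell different in the last year" (6.3, step 2b-ii, stored at step 4e). No planned analysis uses it. Section 6.4.1 announces a comparison of the card with the combined self-assessment. Section 6.4.3.1 lists sensitivity, specificity, accuracy, repeatability and AUC. Neither section defines underestimation or says how it will be analysed.

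**The concern.** The card measures smell only and the hypothesis is about smell only, but a Yes to the self-report item may refer to taste. Among PCR-positive subjects who fail the card, someone who noticed only a change in taste and answers Yes cannot be told apart from someone who noticed the smell loss. The form collects nothing that separates them afterwards. The one-year item does not help: it covers a different period and asks about any difference, not a new loss.

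What is at stake is the reading of the 6.1.1 hypothesis. It claims a gross underestimate, which is a statement about extent, and the combined item does not identify extent. A larger sample would not remove the problem. The main accuracy analysis of the card against PCR is not affected.

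**Working it through.** **1. The plan's own figures.** The documents give no number for this comparison. Their only sample-size figures are the precision figures in 5.3.1 and 6.4.2, and these reproduce with exact (Clopper-Pearson) 95% limits:
- 90/100 gives 82.4% to 95.1%, width 0.127 (plan: 82 to 95%, Table 1 width 0.13).
- 360/400 gives 86.6% to 92.8%, width 0.061 (plan: 87 to 93%, Table 1 width 0.06).
- 34 of the 35 cells in Table 1 match to rounding.

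No figure in the plan is in dispute here.

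**2. What the combined item identifies.** Take the F PCR-positive subjects who fail the card and split them into S (noticed smell loss, with or without taste), T (noticed taste only) and N (noticed neither), so F = S + T + N. Assume truthful answers.
- True under-report fraction: (T + N)/F.
- Fraction seen with the combined item: N/F, because S and T both answer Yes.
- Difference: T/F, which is never negative.

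The observed fraction is therefore a lower bound. Only the sum S + T is observed, so T can lie anywhere from 0 to F − N. Without further assumptions, the true fraction lies anywhere from N/F to 100%.

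**3. Illustration on assumed rates.** From the plan: about 100 PCR-positive outpatients (6.4.2). Assumed: F = 80 card failures, 40 of them truly unaware, and a share r of those 40 answering Yes for taste alone. Observed fraction = 40(1 − r)/80.

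| r | T | N | Observed fraction |
|---|---|---|---|
| 0 | 0 | 40 | 40/80 = 50% |
| 10% | 4 | 36 | 36/80 = 45% |
| 30% | 12 | 28 | 28/80 = 35% |

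The shift is 5 to 15 percentage points. Table 1 gives a full width of 0.20 for a proportion of 0.50 with 100 subjects, a half-width of about 10 points. On these assumptions the bias is of the same order as sampling error.

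**4. Effect on a paired test, also on assumed rates.** Let b be the proportion with card loss and self-report No, and c the proportion with normal card and self-report Yes, with n = 100 and two-sided alpha 0.05. Normal-approximation McNemar power is Φ{[(b − c)√n − 1.96√(b + c)] / √[(b + c) − (b − c)²]}. Take c = 5% throughout. For b = 20% under a smell-only item this is Φ{(1.5 − 0.98)/√0.2275} = 86%. Taste-only Yes answers among card failures lower b:

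| b with smell-only item | no masking | 5% masked | 10% masked | 15% masked |
|---|---|---|---|---|
| 20% | 86% | 61% | 25% | 2.5% |
| 30% | 99% | 97% | 86% | 61% |
| 40% | about 100% | about 100% | 99% | 97% |

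In the top right cell, b falls to 20% − 15% = 5%, equal to c. The net gap vanishes although real under-reporting exists, which is why a null result could not be read. For large gaps with little masking, the loss of power is small.

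**The case against.** The strongest reply is that the cell carrying the hypothesis is sound. A No to the combined question denies smell loss as well as taste loss, so every card-fail/No subject is a valid under-report, and the bias runs against the hypothesis. This stands. A reader might infer that the plan cannot test the hypothesis at all; the documents do not support that reading, because the item gives a conservative test in one direction.

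The item is also the existing CDC question, and beating that question is a stated aim (4.1, 4.2). This stands too, and the item should be kept for that purpose. A reader might further count it as a harm that a taste-only Yes in a card-passing positive raises the question's sensitivity. It is not: that is the question's genuine performance against PCR. Nor does the plan score such a subject as a loss missed by the card, since the card's sensitivity and specificity are defined against PCR. The field at step 4d is itself labelled accurately.

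Third, underestimation is described in 6.1.1 as a related hypothesis. It does not appear in the objectives (4.2), the outcome variables (5.2) or the planned analyses (6.4.3), and the authorization sentence sets no threshold. This limits the weight of the point but does not remove it, because 6.1.1 says the trial seeks to test the premise.

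Finally, a tick-box alone would not supply the missing definition of underestimation. That is right, and the fix includes one.

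**Conclusion.** The point holds as a limit on what can be concluded. The combined item gives a lower bound on under-reporting of smell loss. A positive finding would stand; the extent would not be measured, some power may be lost, and a small or null gap would be ambiguous. The lower-bound argument assumes truthful answers and takes card failure as the measure of smell loss, as the plan does.

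The size of the bias is unknown. The documents give no taste-only rate, and the fall from 50% to 45% or 35% and the power figures rest entirely on assumed inputs. No primary or secondary accuracy estimate against PCR changes. This is a cheap improvement to a stated but subsidiary hypothesis.

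**What to change.** - Keep item 2b-i verbatim as the CDC comparator against PCR.
- Directly beneath it, ask those who answer Yes to tick smell, taste or both, and add one field at step 4d.
- In 6.1.1 and 6.4.3, define underestimation as card failure with smell loss not reported (No, or taste only) among PCR-positive subjects, and report the fraction with a 95% CI.
- Use the combined answer only for the comparison of the device with the CDC question, and correct the labels in 5.2.1 and 6.2.1 that describe it as smell loss alone.
- If the form cannot change, state that the combined item gives a lower bound on under-reporting and that a small or null gap will not be read as evidence of good self-awareness.

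The cost is one tick-box, one data column, a few seconds per subject and an IRB wording amendment.

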6.1.2 Device Administration and Schedule

The device requires minimal preparation. The only key aspect is to not inadvertently damage it and as such would be given in a sealed pouch with a ‘golf pencil’, consent form, instructions and multiple choice answer sheet.

Patients who are in queue for drive-through COVID-19 testing will be approached by a research team member. No prior medical information will be provided to the study team regarding a patient’s eligibility.

The device in a pouch would be given to drive up outpatients that are undergoing PCR testing for COVID. Typically, the device packet would be placed on the test subject’s windshield just as they drive in and are waiting. If the subject consents to take the test, it will only take a minute. They will have the smell test and consent form digitally recorded (by camera) as they hold the test answers against the closed windows while inside the car. They will then give a nasal or oral sample for PCR testing, which is not conducted as part of the study. Of note, the subjects are already undergoing PCR testing and the smell study merely piggybacks on this other scheduled test. Thus there is practically no extra burden.

For the asymptomatic test the same protocol will be used, with the only minor difference is that the test can be replicated multiple times with different variants. As these tests are done in presence of a HCW there is little issue of compliance.

6.1.3 Method of Assignment/Randomization (if applicable)

All drive-through subjects that meet the inclusion/exclusion requirements will be tested.

6.1.4 Device Calibration

There is no gold standard for calibration as every individual responds to odors somewhat differently. But in a healthy population (COVID-19 negative) we expect to get a statistical distribution of results. We will ensure that over time for the control group that the performance of the device is similar and repeat test a random subset of individuals.

6.1.5 Storage Conditions

The device can be stored at ambient temperature (5-40 deg. C) for up to 6 months with negligible loss of performance. Attention should be given to not accidentally scratch the device as this could release some scent. The device should also not get wet. Thus individual devices or bundles thereof will be stored in sealed pouches.

6.1.6 Concomitant therapy

No restrictions at this stage.

6.1.7 Restrictions

No restrictions other than the patient selection criteria.

6.2 Assessments

No guidance available.

6.2.1 Efficacy

The olfactory test enabled from the device will be compared to:

- Patient self-identification for loss of smell: “Do you have any new loss of smell or taste?” YES or NO.
- PCR results for the presence of SARS-CoV-2

The methods for the assessment will be statistical, as described above.

6.2.2 Safety/Pregnancy-related policy

There is minimal safety issues regarding the device EXCEPT the consideration that it may be contaminated by SARS-CoV2 and thus should be treated as hazardous waste. This will be mitigated by having no direct contact with the test material as it will be photographed.

Pregnancy status will be self reported and any pregnant patients will be excluded from the study.

6.2.3 Adverse Events Definition and Reporting

Based on extensive use with scratch-and-sniff™ cards without adverse effects such events would be considered unlikely, nevertheless should they occur they will be immediately reported to the P. I. ([name]). Also the test is fast and non-invasive – highly limiting adverse events.

6.2.4 Pharmacokinetics (if applicable)

None

6.2.5 Biomarkers (if applicable)

The outpatients are already scheduled for RT-PCR testing of SARS-CoV2 which will be typically collected by a swab to the oral/nasal cavity and performed under conditions as mandated by the CDC and PCR test's manufacture directions.

6.3 Study Procedures

For the outpatient drive-up studies the following protocol steps will be performed.

1. As patients drive-up and are still in the car with the windows closed a HCW with suitable PPE will place a ziplock pouch under the wiper of the driver's side windshield. The bag will contain the following materials:
 - a. A consent form
 - b. A pre-sharpened 'golf-pencil'
 - c. The 'u-Smell-it' olfactory device test card
 - d. A multiple choice answer form
2. While in the car, if the patient consents, they will sign the consent form, read the simple instructions (which are also shown as pictograms to make it very easy to follow), take the test, and fill in the answers. This process will take about 1 minute.
 - a. Description of the test: The test card device has 5 windows each printed with a different scent (or no scent) and marked #1, 2, 3, 4, and 5. The test subject merely needs to use their pencil to scratch back and forth 3 times the first window, sniff the window, and looking at the answer score sheet pick the best choice of five choices and fill in the multiple choice circle ("no scent", and scent A, B, C or D). For instance this could be: no scent / apple / orange /

cherry /banana / rose. This procedure will be repeated for each of the 5 windows.

- b. The subject will also be asked on the test if:
 - i. "Do you have any new loss of taste or smell?" (Yes/No)
 - ii. "Does anything smell different in the last year?" (Yes/No)
 - iii. Do you have a stuffy or runny nose? (Yes/No)
- c. If the test site is not part of EPIC the patient will be asked their gender and age band (18-29, 30-39, 40-49, 50-59, 60-69, 70-79, 80+)

3. After the patient completes the test they will pull out the **Consent and Multiple choice questionnaire form**, and with the window still CLOSED hold it up to the driver's side window and it will then be photographed by the attending HCW (likely an ENT resident doctor) whom will add the unique identifier number and add it to the EPIC system.
 - a. [Alternative should there be any issues with the camera or the patient must get out of the car]: The patient will take the completed test packet, place it back in the pouch and under the windshield. The HCW will take the packet and remove the **Consent Form** and **Multiple choice questionnaire form**, check if it is completed (if ask the patient), and place all remaining materials in a biohazard box for destruction. The Consent form and the Questionnaire will be digitalized (scan or photographed) and linked with EPIC so as to be compared to the PCR test results.
4. Information from the uploaded and **Multiple choice questionnaire form** will be entered by a person authorized to access the information into a table that includes:
 - a. Unique identifier
 - b. Gender
 - c. Age band (10 year)
 - d. Y/N to patient self-identified new loss of smell or taste
 - e. Y/N to patient response to "things in the last year smell different"
 - f. Y/N to patient self-identified blocked or stuff nose
 - g. Individual answers on the 5 window smell test
 - h. RT-PCR results for SARS-CoV-2 (+, - or Inconclusive)
 - i. Any other tests for COVID19 (CT or Serological) if given
5. The data will be analyzed in the following fashion:
 - a. Patients that report a blocked or stuffy nose will be excluded from the main analysis (as COVID-19 loss of smell is not due to nasal congestion); but will be analyzed separately to see how this would confound any interpretation.
 - b. Patients that are denoted SARS-CoV-2 "inconclusive" will be excluded from the main analysis; but will be separately analyzed to see if they colocalize with normosmia or anosmia.
 - c. Patients will be split into SARS-CoV-2 positive and negative. As the negative pool is likely to be much larger it will be statistically matched by gender and age profile (potentially with larger bands – e.g. 20 year, depending on the sample size)

- d. The + and - SARS-CoV-2 groups individual performance on the smell test (score 0-5) will be plotted as a histogram. A cutoff will best be chosen to segregate people with normosmia and anosmia (e.g. score = 2 or 3).
- e. False Positives (FP) and False Negatives (FN) will be identified and used to measure the selectivity and sensitivity, respectfully.
- f. Based on the statistical performance (see Table 1) we will determine when we have enough patients to complete the study with a given value of precision.
- g. If a subject fails the smell test (hyposmia or anosmia) but is SARS-CoV-2 negative, yet has other symptoms suggesting being positive for COVID19, we will consider re-testing the subject in 2-3 days by the PCR or serological assay in case the loss of smell precedes a PCR result, or the loss of smell extends past the point in which the viral titer is low and no longer picked up by PCR and would instead be detected by an antibody.

6. The treatment of asymptomatic people will follow an identical protocol with the following differences:
 - a. The study group would consist of high risk subjects that are determined to be positive to SARS-CoV-2 (yet asymptomatic) and the control group would be SARS-CoV-2 negative subject of matching age and gender.
 - b. The smell kit will be directly given to the subject and for HCW the test can be performed at their home.
 - c. There will be a variation of the test in which the order of the scents is altered so that the HCW subject can be re-tested.
 - d. The initial sample size is smaller as this study would firstly see if there was a significant increase of the fraction of anosmia or hyposmia subjects in COVID19+ asymptomatic individuals.

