4.1 Hypothesis

The major hypothesis is that a quantitative and unbiased smell test will be a useful tool to identify COVID-19 positive individuals.

The study will address what fraction of outpatients truly have a loss-of-smell (including a partial loss) and is expected to outperform the current question that is used to identify COVID-19 related anosmia “Do you have a new loss of smell or taste?” (yes/no) in terms of sensitivity and specificity.

The study will address if high-risk asymptomatic people whom are SARS-CoV-2 positive have a partial (or perhaps transitory) loss of smell.

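### The plan does not require the self-report question to be answered before the smell test on the same form, so the test can alter the answer it is compared with.

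*Combined protocol and SAP*

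**What the plan says.** In Section 6.3 step 1 the packet holds a consent form, a pencil, the test card and "A multiple choice answer form". No separate symptom questionnaire is listed.

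In step 2 the subject consents and reads the instructions, and is then to "take the test, and fill in the answers. This process will take about 1 minute". That is the only sequence given. Step 2a describes the windows: scratch, sniff, and "fill in the multiple choice circle ('no scent', and scent A, B, C or D"; then "This procedure will be repeated for each of the 5 windows". Step 2b continues "The subject will also be asked on the test if" and lists three yes/no items: new loss of taste or smell, anything smelling different in the last year, and a stuffy or runny nose. In step 3 the form is photographed after the test is finished. Step 6 applies the same procedure to the asymptomatic cohort, and none of its listed differences concerns this order.

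The first of the three answers is the device's comparator. Section 4.1 says the smell test "is expected to outperform the current question that is used to identify COVID-19 related anosmia". Sections 4.2, 5.2.1, 6.2.1 and 6.4.1 repeat the comparison. Section 6.1.1 adds the hypothesis that "COVID19+ people perform poorly in self-assessments and grossly underestimate their loss of smell", and makes its confirmation one of two conditions for seeking emergency use authorisation.

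**The concern.** As used in practice, the CDC question is answered by someone who has not just taken a smell test. Here the subject may have scratched five windows and personally marked no scent on several of them before answering, or before handing over an answer that can still be changed. The protocol's own premise is that many positive subjects are unaware of their loss. Those are the people whom a smell test could alert.

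Two results are exposed: the device-versus-question comparison, and the hypothesis that positive subjects under-report. Both depend on the pairs in which device and question disagree, and a prompted change of answer removes such pairs. Analysis cannot recover the pre-test answer, because only the final form is captured.

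**Working it through.** **1. What the text fixes about order.**

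| Place | Content | Does it fix the order? |
|---|---|---|
| 6.3 step 2 | Instructions, test, answers | No. The question is not placed in the sequence |
| 6.3 steps 2a to 2c | Windows, then yes/no items, then gender and age | No. This is a list of content |
| 6.3 step 3 | One photograph after completion | No. There is no earlier capture |
| 6.3 step 4 | Data table: gender, age, yes/no answers, then window answers | No. These are table columns |
| 5.1 | Results withheld from subject and staff | No. It does not cover what the subject notices while sniffing |
| 5.2.1 | Odorant order altered for the retest | No. It concerns scents only |

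**2. The plan's own figures.** Section 6.4.2 gives 95% intervals for a sensitivity of 90%. Exact (Clopper-Pearson) limits are 82.4% to 95.1% for 90/100 and 86.6% to 92.8% for 360/400. They agree with the stated 82 to 95% and 87 to 93%. These are single-proportion precisions. The plan gives no figure for the paired comparison, names no test for it, and gives no discordance or switching rate. Everything below is therefore assumed, except n = 100 positives (Section 6.4.2).

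**3. Sensitivity, one-way switching.** Let b be the proportion of positives with device fail and question No, c the reverse, and f the share of the b cell that switches to Yes. Then b = b0(1 − f), d = b − c, and

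power = Φ{[d√n − 1.96√(b + c)] / √(b + c − d²)}, two-sided 0.05.

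- b0 = 0.20, c = 0.05, f = 0: (1.5 − 1.96 × 0.500)/0.477 = 1.09, power 0.862.
- Same, f = 0.3, so b = 0.14: (0.9 − 1.96 × 0.436)/0.4265 = 0.107, power 0.543.

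| f | 20 vs 5: difference, power | 30 vs 5: difference, power |
|---|---|---|
| 0 | 15 points, 0.862 | 25 points, 0.994 |
| 0.1 | 13 points, 0.782 | 22 points, 0.982 |
| 0.2 | 11 points, 0.675 | 19 points, 0.953 |
| 0.3 | 9 points, 0.543 | 16 points, 0.893 |

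**4. Sensitivity, other directions (20 versus 5).** If 30% of the c cell (question Yes, device pass) is instead reassured into No, c = 0.035. The difference rises to 20 − 3.5 = 16.5 points and power to 0.938. If both cells shrink by 30%, the difference is 14 − 3.5 = 10.5 points and power 0.715.

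**5. Specificity.** Assume device specificity 90%, question specificity 95%, and independence among PCR-negatives. Device fail with question No is 0.10 × 0.95 = 0.095. Prompted Yes answers at 30% lower the question's specificity to 0.95 − 0.095 × 0.3 = 92.15%. The device's shortfall shrinks from 5 to 2.15 points. Device pass with question Yes is 0.90 × 0.05 = 0.045. Reassured No answers at 30% raise the question's specificity to 0.95 + 0.045 × 0.3 = 96.35%.

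**The case against.** **The question may already come first.** The printed form and its pictogram instructions are not in the documents. A reader might infer from 2a preceding 2b that the question is asked after the test. The text does not support that: 2a is a description, and the step 4 table lists the yes/no answers ahead of the window answers. List position settles nothing either way. What stands is that no rule requires the question first, and the subject holds the whole form until it is photographed.

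**The primary validation is against PCR.** This is correct. A reader might infer that the device's sensitivity, specificity and accuracy are compromised, but those do not use this answer, and Section 6.4.3.1 does not list the question among its metrics. The comparison with the question is nevertheless part of the primary objective (4.2) and appears under Primary Outcome Variables (5.2.1).

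**The mechanism may be weak.** A window may be printed without scent, so one such mark is not evidence of loss, and a wrong forced choice gives no feedback. A subject with mild hyposmia may notice nothing. This limits the likely size, but a subject who marks no scent on most windows could still notice.

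**The bias is conservative.** For sensitivity with prompted Yes answers, it is: it works against the hypothesis in 4.1. It does not hold for specificity, where the same answers make the question look worse, nor for reassured No answers.

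**Conclusion.** The point holds as a gap in the procedure. The plan allows the comparator answer to be given, or revised, after the test it is compared with. It does not show that this will happen, and the documents give nothing from which to estimate how often.

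The direction is not fixed. Prompted Yes answers understate the device's sensitivity advantage and can lower the question's specificity. Reassured No answers do the opposite.

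The illustrated loss for one-way switching of 0% to 30% is 15 to 9 points with power 86% to 54% (20 versus 5), or 25 to 16 points with power 99% to 89% (30 versus 5). It rests on assumed discordance, assumed switching and a McNemar test that the plan does not specify. With no switching the loss is nil.

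The effect is confined to the device-versus-question comparison and the under-reporting hypothesis, with one exception. The stuffy-nose item sits in the same block, and Section 6.3 step 5a uses it to exclude subjects from the main analysis, so its timing should be protected as well. The change is worth making because it is nearly free and the pre-test answer cannot be recovered later.

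**What to change.** In Section 6.3 step 2, for both cohorts:

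- Print the three yes/no questions at the top of the answer form, before the window items.
- State in the written instructions and the pictograms that they are to be answered before the first window is scratched and not changed afterwards.

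If the printed form already has this layout, the protocol need only say so and add the instruction. A rule that staff refuse late changes is not worth adding: outpatients complete the form behind a closed car window and health care workers may test at home, so staff cannot see changes.

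The cost is form layout and one sentence in 6.3. It needs no extra subjects, staff or testing time.
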